8.1.2.2 Incomplete and Missing Prior and Concomitant Medication Start Date

The following imputation rules will be followed, when the prior and concomitant medication start date is incomplete (eg, only *year* is present, but *month* and *day* are missing) or completely missing:

- If *year* is missing (including the situation where the start date is completely missing), do not impute, and the start date will be treated as missing in the analysis.
- If *year* is present, and *month* and *day* are missing, or *year* and *day* are present, and *month* is missing, set *month* and *day* to January 1st.
- If *year* and *month* are present, and *day* is missing, set *day* to the first day of *month*.

8.1.2.3 Incomplete and Missing Prior and Concomitant Medication End Date

The following imputation rules will be followed, when the prior and concomitant medication end date is incomplete (e.g., only *year* is present, but *month* and *day* are missing) or completely missing:

- If it is indicated that the medication is ongoing (ie, “Yes” is checked for the question “Ongoing?” in the CRF), do not impute, since there should not be an end date for this medication.
- If *year* is missing (including the situation where the end date is completely missing), do not impute, and the end date will be treated as missing in the analysis.
- If *year* is present, and *month* and *day* are missing, or *year* and *day* are present, and *month* is missing, set *month* and *day* to December 31st.
- If *year* and *month* are present, and *day* is missing, set *day* to the last day of *month*.

8.2 Baseline and Study Day Definitions

8.2.1 Baseline Date (Study Day 1)

Baseline is defined as the earliest date of the first dose of defibrotide or conditioning therapy.

8.2.2 Baseline Value

For assessments where time was collected for both the assessment and the first dose, the baseline value is defined as the last nonmissing value collected on or before the time of the first dose. For assessments where time was not collected, the baseline value is defined as the last nonmissing value collected on or before the date of the first dose. For subjects who do not have at least one dose of defibrotide or conditioning therapy, the baseline value is defined as the value that was collected where nominal Visit = Baseline. If this value is missing, then baseline value is defined as the value collected where Visit = Screening.

8.2.3 Day +0 Post-HSCT

Day +0 post-HSCT is defined as the 0th day after HSCT; that is, the day of HSCT. For subjects in the ITT Analysis Set who do not have HSCT, Day +0 post-HSCT is the 0th day after randomization; that is, the day of randomization. For the analyses of all efficacy endpoints, duration calculations will start at Day +0 post-HSCT.

8.2.4 Day +X Post-HSCT

Day +X post-HSCT is defined as the Xth day after the date of Day +0 post-HSCT, where X is a positive integer representing the number of days to an event. For subjects who do not undergo HSCT, Day +X post-HSCT is the Xth day after the date of randomization. Day +X post-HSCT for an event is calculated as follows:

$$X = [\text{Date of the event}] - [\text{Date of Day +0 post-HSCT}]$$

8.2.5 Post-VOD Treatment Day

Day +0 post-VOD Treatment is defined as the VOD Treatment initiation date after VOD diagnosis. Post-VOD Treatment day is calculated relative to Day +0 post-VOD Treatment. For events that occurred after the VOD Treatment date (i.e. Day +X post-VOD Treatment), the day is calculated as follows:

$$X = [\text{Date of the event}] - [\text{Date of Day +0 post-VOD Treatment}]$$

8.3 Study Phase

In this study, the occurrence of VOD and the administration of rescue defibrotide represent a clinical landmark time point for safety. Therefore, for the safety analyses, 2 study phases are defined with respect to the administration of rescue defibrotide, as follows:

- **Prophylaxis Phase:**
 - If VOD occurs, the prophylaxis phase starts on the Baseline date and ends on the day before the start date of rescue defibrotide (ie, rescue treatment start date – 1).
 - If VOD does not occur, the prophylaxis phase starts on the Baseline date and ends on the date of study completion/early termination.
- **Rescue Treatment Phase:**
 - For the subset of subjects who developed VOD and received rescue defibrotide, the rescue treatment phase begins on the start date of rescue defibrotide and ends on the date of study completion/early termination.

The start date of rescue defibrotide will be derived as the date of the first administration of defibrotide on or after the investigator diagnosis of VOD.

Unless otherwise noted, safety summaries will be reported by study phase and by treatment received during the Prophylaxis Phase.

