The safety of defibrotide 25 mg/kg/day as prophylaxis has been demonstrated in children undergoing myeloablative conditioning considered to be at high risk of developing VOD (Corbacioglu et al. 2012). Incidences of AEs, serious adverse events (SAEs), and events leading to discontinuation were similar between the defibrotide and control groups (207 SAEs in 108 patients in the defibrotide group and 231 SAEs in 103 patients in the control group). Although the most common AE considered by the investigator to be related to defibrotide was hemorrhage, the cumulative incidence of hemorrhage was similar between groups (39 [22%] of 177 patients in the defibrotide group vs 37 [21%] of 176 patients in the control group;  $p=0.8176$ ). Overall, most fatal AEs were either neoplasms (12 [7%] of 177 patients in the defibrotide group and 14 [8%] of 176 patients in the control group) or infections (6 [3%] patients in the defibrotide group and 11 [6%] patients in the control group). In the intent-to-treat (ITT) population, patients who underwent allogeneic HSCT and who received defibrotide prophylaxis had a lower overall incidence of acute graft-versus-host disease (GvHD) (all grades) by Day +30 and +100 post-HSCT compared with those in the control group (Day +30 post-HSCT, 34% vs 53%  $p=0.004$ ; Day +100 post-HSCT, 47% vs 67%  $p=0.002$ ). A lower incidence of acute GvHD was also observed when grade 1 toxicity was excluded.

Defibrotide (JZP-381)  
Clinical Trial Protocol: 15-007 Version 4.0

Jazz Pharmaceuticals, Inc.  
20 August 2018

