#### 5.2.1.2 Defibrotide Rescue Treatment for Patients who Develop VOD

For patients who develop VOD per modified Seattle criteria in either the DP or BSC arms, defibrotide will be administered as treatment for VOD until resolution of VOD or hospital discharge, whichever is sooner, and may continue beyond Day +30 post-HSCT. Patients must be hemodynamically stable and not at risk of bleeding, as defined in the first 3 exclusion criteria (#1, #2, #3) listed in [Section 4.2](#), to receive defibrotide as rescue treatment for VOD. Patients with VOD undergoing rescue treatment with defibrotide will continue to receive individualized standard of care therapy (BSC) based on local institutional guidelines and patient need. Medications that increase risk of bleeding must be stopped 24 hours prior to the start of defibrotide rescue treatment (see [Section 5.7.6](#)).

Defibrotide administration must be stopped if a patient has clinically significant bleeding. Defibrotide may be re-initiated if the bleeding is controlled and is of severity  $\leq$  grade 1.

The daily dose of defibrotide in patients who receive rescue treatment with defibrotide after being randomized to the DP or BSC arm will be based on body weight at baseline (i.e., within 24 hours before conditioning begins for the DP arm, and on the day that conditioning begins for patients in the BSC arm who develop VOD and subsequently receive defibrotide).

Defibrotide (JZP-381)  
Clinical Trial Protocol: 15-007 Version 4.0

Jazz Pharmaceuticals, Inc.  
20 August 2018

---

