### 6.8.1 Adverse Events

#### 6.8.1.1 Reporting of Adverse Events

An AE is any untoward medical occurrence associated with the use of a drug in humans, whether or not considered related to study drug or procedure.

Adverse events include, but are not limited to, the following: (1) a worsening or change in nature, severity, or frequency of conditions present at the start of the study; (2) patient deterioration due to primary illness; (3) intercurrent illness; (4) drug interaction; and/or (5) clinically significant laboratory values.

All AEs, whether observed by the investigator, reported by the patient, determined from laboratory findings, or other means, will be recorded.

Patients should be questioned in a general way, without asking about the occurrence of any specific symptom. The investigator should attempt to establish a diagnosis of the event based on signs, symptoms, and/or other clinical information. In such cases, the diagnosis, not the individual signs/symptoms, should be documented as the AE.

Following questioning and evaluation, all AEs, whether believed by the investigator to be related or unrelated to the study drug or procedure, must be documented in the patient's medical records, in accordance with the investigator's normal clinical practice. Each AE is to be evaluated for duration, severity, seriousness, outcome, action taken with study drug, and causal relationship to the study drug or procedure.

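### SAP 8.3 can date DP rescue from the next routine prophylaxis dose, so a VOD event arising on drug drops out of the DP Prophylaxis-Phase tables while the same event can stay in the BSC tables

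*SAP*

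**What the plan says.** SAP 8.3 defines two phases for safety. For a patient with VOD the first is set as follows: "If VOD occurs, the prophylaxis phase starts on the Baseline date and ends on the day before the start date of rescue defibrotide". For those who receive rescue, "the rescue treatment phase begins on the start date of rescue defibrotide". The date that drives both is derived: "start date of rescue defibrotide will be derived as the date of the first administration of defibrotide on or after the investigator diagnosis of VOD". Protocol 9.14 has the same end-date rule (rescue start minus one day) but not the derivation. SAP 8.3 and SAP 11 then report safety by arm and phase.

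Prophylaxis is infused every six hours (SAP 4.4). At least 21 days is recommended, roughly to Day +15, with Day +30 as the latest end (Protocol 1.3).

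In either arm, before rescue, "Medications that increase risk of bleeding must be stopped 24 hours prior to the start of defibrotide rescue treatment" (Protocol 5.2.1.2). Such drugs are allowed in BSC alone but barred during defibrotide (Protocol 5.7.6). Rescue drug is released after a yes/no confirmation in IWRS that the VOD criteria are met (Protocol 3.1).

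On recording, Protocol 6.8.1.1 says: "All AEs, whether observed by the investigator, reported by the patient, determined from laboratory findings, or other means, will be recorded". VOD is not among the exclusions listed in Protocol 6.8.1.3. SAP 11.2 places treatment-emergent events by onset date. No section says to which phase the VOD event itself belongs.

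**The concern.** The derivation treats any defibrotide dose as rescue once VOD is diagnosed. A DP patient on uninterrupted prophylaxis is dosed on the diagnosis date whether or not rescue has begun. The Prophylaxis Phase therefore closes the day before, and anything with onset on the diagnosis date goes to the Rescue Phase. A BSC patient has no dose until rescue is released and given. If that is the next day or later, the same event counts in the Prophylaxis Phase.

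The Prophylaxis-Phase tables carry the randomised safety comparison. If VOD enters them as an adverse event, the VOD row and the serious and Grade 3-4 rows depend on whether the patient was already on drug, and not only on what happened. Any other event with onset that day, a bleed for example, moves in the same way.

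**Working it through.** The plan states no figure to reproduce. The check applies the date rule and then sizes its effect.

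**Date rule.** D is the investigator's diagnosis date. Rescue start is the earliest dose date on or after D. The last Prophylaxis day is rescue start minus 1.

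| Case | Event onset | Derived rescue start | Last Prophylaxis day | Phase of event |
|---|---|---|---|---|
| DP, still dosed | D | D | D-1 | Rescue |
| DP, still dosed | D-1 | D | D-1 | Prophylaxis |
| DP, prophylaxis ended or held, rescued D+1 | D | D+1 | D | Prophylaxis |
| BSC, rescued on D | D | D | D-1 | Rescue |
| BSC, rescued on D+1 | D | D+1 | D | Prophylaxis |
| BSC, rescued on D+2 | D | D+2 | D+1 | Prophylaxis |

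The arms differ when rows 1 and 5 or 6 are the typical cases.

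**VOD row.** Let p be true VOD incidence and s the share of VOD cases with a defibrotide dose on D. Assume the event is recorded with onset on D and that cases never rescued stay in the Prophylaxis Phase. The Prophylaxis-Phase VOD rate is then p × (1 − s). Inputs: p = 20% (35 of 176 controls) and 12% (22 of 180 on defibrotide) from the earlier randomised trial in Protocol 1.2; 200 per arm from SAP 4.6. The documents do not give s, so it is varied.

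| True VOD, DP / BSC | s in DP | s in BSC | Shown, DP / BSC | Shown gap (BSC − DP) | True gap |
|---|---|---|---|---|---|
| 20% / 20% | 100% | 0% | 0% / 20% (0 / 40 patients) | 20 | 0 |
| 20% / 20% | 100% | 50% | 0% / 10% (0 / 20) | 10 | 0 |
| 20% / 20% | 100% | 100% | 0% / 0% | 0 | 0 |
| 20% / 20% | 50% | 0% | 10% / 20% | 10 | 0 |
| 20% / 20% | 50% | 100% | 10% / 0% | −10 | 0 |
| 12% / 20% | 100% | 0% | 0% / 20% | 20 | 8 |
| 12% / 20% | 100% | 50% | 0% / 10% | 10 | 8 |
| 12% / 20% | 100% | 100% | 0% / 0% | 0 | 8 |

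The distortion is shown gap minus true gap = p(DP) × s(DP) − p(BSC) × s(BSC). With 12%, 20% and s(DP) = 100% it is zero at s(BSC) = 12/20 = 60%. Above that, the table is less favourable to DP than the truth.

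**Any-SAE row, illustrative.** The earlier trial reported "207 SAEs in 108 patients in the defibrotide group and 231 SAEs in 103 patients in the control group" (Protocol 1.3), against group sizes of 177 and 176. Assume that every VOD is serious, that VOD is independent of other SAEs, and that these rates stand for other SAEs.

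- BSC: 0.20 × (1 − 103/176) = 0.20 × 0.415 = 8.3 points added by VOD.
- DP: 0.12 × (1 − 108/177) = 0.12 × 0.390 = 4.7 points.
- Correct difference: 8.3 − 4.7 = 3.6 points.
- Shown if all DP cases are dosed on D and 25% to 75% of BSC rescues start later: DP 0; BSC 8.3 × 0.25 = 2.1 to 8.3 × 0.75 = 6.2.
- Net distortion: 2.1 − 3.6 = −1.5 to 6.2 − 3.6 = +2.6 points.

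With an assumed 22% VOD in BSC, the same steps give 0.22 × 0.415 = 9.1, a correct difference of about 4.4 or 4.5 points depending on rounding, and a net distortion of about −2.2 to +2.4 points.

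**The case against.** The strongest reply is that the arms may be treated alike more often than the mechanism suggests. Protocol 7.4 wants rescue begun promptly after diagnosis, so same-day BSC rescue is possible. The IWRS step carries no stated delay. The 24-hour stop matters only for patients on bleeding-risk drugs, and heparin up to 100 U/kg/day is allowed in both arms. DP patients are not all on drug at diagnosis: prophylaxis may have ended from about Day +15, or been held or stopped for bleeding. If onset is recorded before the diagnosis date, a DP event stays in the Prophylaxis Phase as well. All of this stands, and it limits the size and leaves the direction open. It does not remove the fault, because the written rule still gives different phases for the same event according to prior dosing.

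A reader might infer that the rule inflates BSC adverse-event rates. It does not: BSC VOD is never counted above its true incidence, and the error is events moved out of the DP Prophylaxis rows.

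A reader might also infer that it makes defibrotide look safer and hides harm. The documents do not show this. The net effect can run either way, VOD would be visible as its own preferred-term row, and VOD by arm is reported under SAP 10.1.3 and 10.2.2.1. The special-interest lists for bleeding and hypersensitivity contain no VOD term, although a bleed with onset on the diagnosis date is still subject to the phase rule.

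Nor is this the primary endpoint leaking into safety. The phase date uses the investigator's diagnosis, whereas the endpoint uses the adjudication committee's (SAP 4.3.1).

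**Conclusion.** The concern holds in a limited form. For DP patients still being dosed, SAP 8.3 sets rescue start to the diagnosis date, so events with onset that day leave the Prophylaxis Phase. BSC patients first dosed later keep them. If VOD is recorded as an adverse event, which the documents neither state nor exclude, DP VOD is undercounted relative to BSC in the Prophylaxis-Phase tables, and the serious and Grade 3-4 rows are not comparable between arms.

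In the VOD row the spurious gap is 20, 10 or 0 points under equal 20% incidence, all DP cases on drug, and 0%, 50% or 100% same-day BSC rescue. With only half of DP cases on drug it runs from +10 to −10. The any-SAE effect is a few points in either direction and rests on assumed independence, on every VOD being serious, and on earlier-trial SAE rates that may already include VOD. The two shares that fix size and direction are not in the documents. The plan should be changed on this point, but no claim that it favours one arm is warranted.

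**What to change.** Keep the phase cut at rescue start and change three things.

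1. State in SAP 8.3 that the investigator-diagnosed VOD event, and other adverse events with onset on the diagnosis date before rescue is started, belong to the Prophylaxis Phase in both arms. If onset times are not collected, give one date convention for both arms.
2. For the DP arm, define rescue start as the recorded start of rescue (IWRS), not the next continuing prophylaxis dose. This does not replace item 1: Protocol 7.4.1.1 schedules the IWRS registration at diagnosis, so the two dates may often coincide.
3. Add overview rows for any treatment-emergent, serious and Grade 3-4 events that exclude VOD.

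Moving the whole phase cut to the diagnosis date would be the wrong repair. Rescue is optional (SAP 4.1) and the Rescue Phase is defined by receipt of rescue drug, so patients never rescued would be placed in a phase they do not fit. The same edit could give an end date for those patients' Prophylaxis Phase, which SAP 8.3 leaves open.

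The cost is a few lines of SAP text, a few extra table rows, and a small departure from Protocol 9.14 to be noted in SAP 5.

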## 9.14 Safety Endpoints and Analyses

Safety analyses will be conducted using the safety population.

In this study, the occurrence of VOD and the administration of rescue defibrotide represent a clinical landmark time point for safety. Therefore, for the safety analyses, 2 study phases are defined with respect to the administration of rescue defibrotide, as follows:

- Prophylaxis Phase – For the overall safety population, this phase is defined as the period between baseline and start date of rescue defibrotide, if applicable, or the period between baseline and Day +180 post-HSCT if no VOD occurred. (End date of Prophylaxis Phase=start date of rescue defibrotide – 1, or Day +180 post-HSCT if no VOD occurred)
- Treatment Phase – For the subset of patients in the safety population who developed VOD and received rescue defibrotide, this phase is defined as the period between start date of rescue defibrotide and Day +180 post-HSCT. (Start date of Treatment Phase=start date of rescue defibrotide)

Patients will be analyzed by study phase and by treatment received during the Prophylaxis Phase.

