### 9.14.1 Adverse Events

Adverse events will be coded using the Medical Dictionary for Regulatory Activities (MedDRA) to classify events under primary system organ class and preferred term.

The number and percentage of patients who experienced treatment-emergent adverse events (TEAEs), serious TEAEs, TEAEs leading to discontinuation of study drug, Grade 3 and 4 TEAEs, and deaths will be summarized by study phase and treatment received during the Prophylaxis Phase. Results will be presented by system organ class and preferred term. The overview will also report TEAEs by maximum severity.

The number and percentage of patients with treatment-related TEAEs, serious TEAEs, TEAE leading to discontinuation, Grade 3 and 4 TEAEs, and patients who have died will also be summarized by study phase and treatment received during the Prophylaxis Phase.

For all AE summaries, if a patient has more than 1 AE within a preferred term, the patient is counted only once at the maximum severity and with the closest relationship to study drug. If a patient has more than 1 AE within a system organ class, the patient is similarly counted once when reporting results for that system organ class.

Defibrotide (JZP-381)  
Clinical Trial Protocol: 15-007 Version 4.0

Jazz Pharmaceuticals, Inc.  
20 August 2018

---

All AE data will be listed. The information presented will include patient number, treatment, primary system organ class and preferred term, date of onset, severity, relationship to study drug, action taken, and stop date (if available).

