11 SAFETY

Safety summaries will be provided by treatment arm and study phase based on the Safety Analysis Set.

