11.2 Adverse Events

Adverse events recorded in the case report form will be coded to SOC and PT using the MedDRA 19.1. The investigator will assess the relatedness of each AE to study drug. The severity of AEs will be recorded using the Common Terminology Criteria for Adverse Events (CTCAE 4.03).

At a minimum, for subjects in either the DP or BSC arm, the investigator must record all AEs and SAEs that occur from the time written informed consent is obtained until screen failure if applicable, or Day +60 post-HSCT, regardless of their relationship to study drug or procedure. Even if the minimum of Day +60 post-HSCT is met, the investigator must continue to record all AEs and SAEs that occur within 30 days after the last dose of defibrotide, regardless of their relationship to study drug or procedure. For subjects who do not receive HSCT, AEs must be collected for 70 days after Baseline or early termination, whichever occurs first. For subjects randomized but not treated, AEs will be collected for 70 days after randomization or early termination, whichever is earlier. Any SAE assessed as related to defibrotide or study procedures by the investigator should be reported regardless of time after study termination. Related SAEs reported after study termination will be collected in the Safety database only.

A treatment-emergent adverse event (TEAE) is defined as any event with onset date on or after the first dose of study treatment (either DP or conditioning regimen) or any ongoing event that worsens in severity after the date of the first dose of study treatment through the protocol-specific reporting period. Only TEAEs with the onset date on or before the end of the protocol-specific AE reporting period noted above will be included in summary tables unless otherwise specified. All AEs will be listed. For the purpose of calculating treatment emergence, incomplete onset dates will be imputed as detailed in Section [8.1.2.1](#).

AEs are graded by the investigator as Grade 1 (mild), Grade 2 (moderate), Grade 3 (severe), Grade 4 (life threatening), or Grade 5 (fatal). The severity grade of events for which the investigator did not record severity will be categorized as “missing” for tabular summaries and data listings, and will be considered the least severe for the purposes of sorting for data presentation.

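### Adverse-event percentages are taken over a Prophylaxis Phase that rescue shortens; if rescue is more frequent in the BSC arm, defibrotide will look modestly more toxic than it is

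*SAP*

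**What the plan says.** SAP 8.3 splits follow-up at rescue: "If VOD occurs, the prophylaxis phase starts on the Baseline date and ends on the day before the start date of rescue defibrotide". For other patients, "If VOD does not occur, the prophylaxis phase starts on the Baseline date and ends on the date of study completion/early termination". The rescue start is "derived as the date of the first administration of defibrotide on or after the investigator diagnosis of VOD". By default, "safety summaries will be reported by study phase and by treatment received during the Prophylaxis Phase"; Protocol 9.14 agrees: "Patients will be analyzed by study phase and by treatment received during the Prophylaxis Phase". SAP 11 repeats it: "Safety summaries will be provided by treatment arm and study phase based on the Safety Analysis Set".

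The AE measure is the number and percentage of patients (Protocol 9.14.1, SAP 11.2). The main tables are limited to the AE reporting period, which runs at least to "Day +60 post-HSCT, regardless of their relationship to study drug or procedure", and to 30 days after the last defibrotide dose if that is later. SAP 11.1 derives days of drug exposure but does not use them as an AE denominator. SAP 11.2 lists no time-to-event AE analysis and no AE table stated to pool the phases by arm. The overall TEAE summary is not defined as pooled. The extra table of events recorded outside the reporting period lengthens the calendar window, but nothing says that it lifts the phase split.

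**The concern.** Comparing the safety of defibrotide plus BSC with BSC alone is a stated objective (SAP 4.2.2). A crude percentage understates risk in whichever arm is followed for less time. Here the end of follow-up depends on VOD, the outcome that prophylaxis is meant to reduce. The better the drug works, the longer its patients stay in the phase and the more background AEs are counted against it. The split also places events after rescue, including deaths, in a subset selected by outcome. A reader who takes the Prophylaxis Phase columns as the between-arm comparison could therefore see an excess on defibrotide that comes only from unequal observation time.

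**Working it through.** The plan gives no figure for the AE comparison, so there is none to reproduce. Its design rates are consistent with each other: ln(0.86)/ln(0.72) = 0.459, the stated hazard ratio of 0.46.

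**Inputs from the documents**
- Earlier randomised trial, VOD by Day +30: 22/180 = 12.2% defibrotide, 35/176 = 19.9% control (Protocol 1.2).
- Design rates, VOD or death by Day +30: 14% DP, 28% BSC (SAP 4.6). These are an upper bound for rescue, because death does not trigger it.
- AE reporting to Day +60 (SAP 11.2). Conditioning of about 5 days, with baseline up to a day earlier (Protocol 1.3), gives a window of about 66 days.

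**Assumptions**
- Every VOD case is rescued. The plan gives no phase end for a VOD patient who is not rescued.
- Rescue falls uniformly on Days +3 to +28, so time from baseline to rescue T runs from 9 to 34 days (mean 21.5).
- The AE hazard is equal in the two arms.

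**Mean phase length within the window**
- 14%/28%: DP 0.86 × 66 + 0.14 × 21.5 = 59.8 days; BSC 0.72 × 66 + 0.28 × 21.5 = 53.5 days.
- 12.2%/19.9%: 60.6 and 57.2 days by the same sum.

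**Formula.** Let p be the full-window AE risk, L = −ln(1 − p), and v the share rescued. A rescued patient's chance of an AE before rescue is q = mean over T of 1 − exp(−L·F(T)). F(T) is T/66 for a constant hazard, and (1 − 2^(−T/10))/(1 − 2^(−66/10)) for a hazard with a 10-day half-life. The observed share is (1 − v)p + v·q, so the spurious excess on DP is (v_BSC − v_DP)(p − q).

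| p | q, constant | q, 10-day half-life |
|---|---|---|
| 20% | 0.070 | 0.154 |
| 40% | 0.152 | 0.318 |
| 60% | 0.254 | 0.495 |

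The difference in share rescued is 0.1989 − 0.1222 = 0.0766 at the earlier trial's rates and 0.14 at the design rates. For p = 40% and constant hazard this gives 0.0766 × 0.248 = 1.90 points and 0.14 × 0.248 = 3.47 points. In full:

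| Spurious excess on DP, points | p = 20% | 40% | 60% |
|---|---|---|---|
| 12.2%/19.9%, constant hazard | 1.00 | 1.90 | 2.65 |
| 14%/28%, constant hazard | 1.82 | 3.47 | 4.84 |
| 12.2%/19.9%, 10-day half-life | 0.35 | 0.63 | 0.80 |
| 14%/28%, 10-day half-life | 0.64 | 1.15 | 1.47 |

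**Rescue timing.** With rescue on Days +7 to +21 and constant hazard, a 30% AE shows an excess of 1.5 points (earlier trial) and 2.8 points (design rates). The result is not sensitive to this choice.

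**Rescue uptake.** With 70% uptake in BSC and full uptake in DP at 14%/28%, the BSC share falls to 0.28 × 0.7 = 19.6%, and the excess to 0.7, 1.4 and 1.9 points. It is zero when BSC uptake relative to DP is 14/28 = 50%, or 12.2/19.9 = 61% at the earlier trial's rates, and reverses below that.

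**If VOD raises AE risk.** Suppose the AE hazard doubles from VOD at Day +14 (T = 20 days), with a 30% full-window risk otherwise and 14%/28% rescued. Over the whole window the risk is 32.2% DP vs 34.3% BSC. The Prophylaxis Phase shows 27.2% vs 24.5%, so the sign of the comparison changes.

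**The case against.** The phases exist for a good reason. Rescued BSC patients receive defibrotide at the prophylaxis dose (Protocol 5.3), and counting their later bleeding or hypersensitivity as BSC events would contaminate the control and could hide harm from the drug. That stands: the phase tables should stay, and a by-arm table over a fixed window is a supplement.

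Rescue is also not the same as VOD. It is optional, follows the investigator's diagnosis, and requires haemodynamic stability and no bleeding risk (Protocol 5.2.1.2), while drugs that raise bleeding risk are allowed in the BSC arm (Protocol 5.7.6). A DP patient still on prophylaxis can meet the rescue-start definition on the day of diagnosis, whereas a BSC patient needs a new start. These features would tend to reduce the bias. The AE tables are descriptive, and the expected bias runs against the sponsor's drug.

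A reader might infer more than the documents support:
- **That the excess is firmly 1.8-4.8 points.** This needs rates that include deaths, full rescue uptake and a constant hazard. The documents give no AE timing, and toxicity from conditioning may well come early.
- **That the truncated patients are the sickest.** This is plausible, but nowhere documented.
- **That events after rescue are lost.** They are tabulated in the rescue phase by the treatment received during prophylaxis.
- **That no outcome is analysed by arm across rescue.** VOD-free survival, non-relapse mortality (malignant disease only) and engraftment are analysed by arm (SAP 10 and 11.6). The gap concerns the AE tables. The table shells are in a separate document, so the layout of the overall TEAE summary is not known.
- **That events per person-time would remove the bias.** With equal hazards of 10-day half-life at 14%/28%, that rate gives a DP/BSC ratio of about 0.93 (0.96 with a 20-day half-life), which makes defibrotide look spuriously safer.

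**Conclusion.** The point holds in a limited form. The Prophylaxis Phase percentages do not compare the arms over equal time, and nothing stated in the protocol or SAP corrects this. If rescue is more frequent in the BSC arm, as the design expects, the error runs against defibrotide. For AEs of 20-60% risk to Day +60 it is about 1.0-2.7 points at the earlier trial's VOD rates, at most about 1.8-4.8 at the design rates, and about 0.4-1.5 if AEs cluster early. These figures depend on assumed rescue timing, hazard shape and uptake. The primary efficacy analysis is unaffected. This is a cheap improvement and does not make the planned tables unusable.

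**What to change.** Keep the phase tables and add two things to SAP 11.2.

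1. Summaries of TEAEs, serious TEAEs, AEs of special interest and deaths by arm over fixed common windows, baseline to Day +30 and baseline to Day +60, regardless of rescue. Label them a supplementary between-arm comparison to be read alongside the phase tables. State the drawback, that BSC events after rescue include defibrotide exposure, and flag those events in the table.
2. For the pre-rescue comparison, a time-to-first-AE summary by arm, censored at rescue. Prefer this to a simple events-per-person-time rate, which is unbiased only under a constant hazard. Note that censoring at rescue may be informative, because rescue follows VOD.

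The SAP should also say whether the overall TEAE summary pools the phases. The cost is a few programmed tables. AEs are already collected in both arms to at least Day +60 whether or not rescue is given, and start dates are listed for every event.
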